11.2 Serious Adverse Events

A serious adverse event (SAE) is any untoward medical occurrence that at any dose meets 1 or more of the following criteria:

- Is fatal
- Is life threatening
 - *Note: Life-threatening refers to an event that places the patient at immediate risk of death. This definition does not include a reaction that, had it occurred in a more severe form, might have caused death*

 Catalyst <small>pharmaceuticals</small>	CMS-001 Version Amendment 5	Page 58
---	---------------------------------------	----------------

- Requires or prolongs in-patient hospitalization
- Results in persistent or significant disability or incapacity
- Is a congenital anomaly or birth defect, that is, an AE that occurs in the child or fetus of a patient exposed to IP prior to conception or during pregnancy
- Is an important medical event or reaction.

For this study, a generalized tonic-clonic convulsion/seizure is to be considered an SAE.

The reporting period for SAEs begins after informed consent is obtained and continues through 4 weeks after the last dose or at the early discontinuation visit.

Any SAE, whether or not considered related to study drug, must be reported within 24 hours of knowledge of the event by forwarding (fax, email) the study-specific SAE Report Form to Catalyst. As additional information becomes available, including but not limited to the outcome of the SAE and any medication or other therapeutic measures used to treat the event, it must be reported within 24 hours to Catalyst.

The investigator should follow all unresolved SAEs until the events are resolved or stabilized, the patient is lost to follow-up, or it has been determined that the study treatment or participation is not the cause of the AE. Resolution of AEs (with dates) should be documented in the eCRF and in the patient's medical record.

For some SAEs, Catalyst may follow up by telephone, fax, email, and/or a monitoring visit to obtain additional case details deemed necessary to appropriately evaluate the SAE report (e.g. hospital discharge summary, consultant report, autopsy report).

At the last scheduled visit, the investigator should instruct each patient to report any subsequent SAEs that the patient's personal physician(s) believes might be related to prior study treatment.

The investigator should notify Catalyst of any death or SAE occurring at any time after a patient has discontinued, or terminated study participation, if felt to be related to prior study treatment. Catalyst should also be notified if the investigator should become aware of the development of cancer, or of a congenital anomaly, in a subsequently conceived offspring of a patient that participated in this study.

Reporting of SAEs to the IRB, IEC or REB will be done in compliance with the standard operating procedures and policies of the IRB, IEC or REB and with applicable regulatory requirements. Adequate documentation must be provided showing that the IRB IEC or REB was properly and promptly notified as required.

 Catalyst pharmaceuticals	CMS-001 Version Amendment 5	Page 59
--	--------------------------------	---------

11.3 Safety Blood Collection

Patients who experience a serious or severe AE should have, at the discretion of the investigator, a blood sample drawn for safety labs as soon as possible after the AE.

Additional blood sampling may be performed at any time during the study if warranted to monitor patient safety.

11.4 Pregnancy

Pregnancy in a patient or partner should be reported within 24 hours of the site becoming aware of the pregnancy by fax or email of the Pregnancy Reporting Form, in the study reference materials, to Catalyst. In addition, pregnancy in a patient is also reported on the End of Study CRF. The investigator must make every effort to follow the patient through resolution of the pregnancy (delivery or termination) and to report the resolution on the follow-up form (Pregnancy Reporting Form: Additional Information) in the study reference materials. In the event of pregnancy in the partner of a study patient, the investigator should make every reasonable attempt to obtain the woman's consent for release of protected health information.

11.5 Urgent Safety Measures

The regulations governing clinical trials state that the sponsor and investigator are required to take appropriate urgent safety measures to protect subjects against any immediate hazards that may affect the safety of subjects, and that the appropriate regulatory bodies should be notified according to their respective regulations. According to the European Union (EU) Clinical Trial Directive 2001/20/EC, "...in the light of the circumstances, notably the occurrence of any new event relating to the conduct of the trial or the development of the investigational medicinal product where that new event is likely to affect the safety of the subjects, the sponsor and the investigator shall take appropriate urgent safety measures to protect the subjects against any immediate hazard. The sponsor shall forthwith inform the competent authorities of those new events and the measures taken and shall ensure that the IRB/EC/REB is notified at the same time." The reporting period for urgent safety measures is the period from the time of signing of the ICF through the completion of the last study visit. Investigators are required to report any urgent safety measures within 24 hours.

 Catalyst pharmaceuticals	CMS-001 Version Amendment 5	Page 60
--	--------------------------------	---------

Examples of situations that may require urgent safety measures include discovery of the following:

- An immediate need to revise IP administration (i.e. modified dose amount or frequency not defined in protocol).
- Lack of study scientific value, or detrimental study conduct or management.
- Discovery that the quality or safety of IP does not meet established safety requirements.

12 APPROPRIATENESS OF MEASUREMENTS

The measures of safety used in this study are routine clinical and laboratory procedures. The efficacy measures use a variety of approaches to evaluate changes in neuromuscular function and muscle strength. These standardized tests have been previously used for determination of response to therapeutic intervention in patients with MG and in other indications and, thus, are relevant for use in this study in patients with CMS.

 Catalyst pharmaceuticals	CMS-001 Version Amendment 5	Page 61
---	--------------------------------	---------

13 STUDY PROCEDURES

13.1 Screening Visit

An ICF must be signed and dated by the patient, parent or legal guardian, the investigator or designee, and witness (if required) before any study-related procedures are performed. Refer to Section 10.4 for prohibited medications.

After ICF signed, the patient will be screened for enrollment into the study. The study activities listed below will be performed during the 1 to 14 days that constitute the Screening visit.

- Informed Consent;
- Assessment of Inclusion/Exclusion criteria;
- Demographics (sex, race, ethnic origin, age);
- Medical history, including allergy history and number of hospitalizations or ER visits in last 6 months;
- CMS genetic testing, if not previously done and report available;
- Standard resting 12-lead ECG;
- Complete physical examination including weight and height;
- Vital signs (seated position), including systolic blood pressure (SBP), diastolic blood pressure (DBP), heart rate, respiration, and body temperature;
- Clinical laboratory tests;
- For females of child bearing potential, a serum pregnancy test will be taken at Screening.;
- MFM 20 or 32;
- Stimulated single fiber EMG (optional);
- CGI-S;
- Slurp test (optional);
- Assessment of SAEs; and
- Assessment of concomitant medications.

13.2 Open-label Run-in

Patients, previously not on amifampridine phosphate treatment for CMS may visit the study site for weekly visits for up to 4 weeks throughout the run-in period for the assessments and

 Catalyst pharmaceuticals	CMS-001 Version Amendment 5	Page 62
--	--------------------------------	---------

procedures listed in [Table 3](#). Efficacy measurements will be performed during or at the end of run-in to document improvement or maintenance of optimal benefit of study drug. Additional visits or telephonic interactions are allowed as necessary.

At the end of this period (Day 0), patients must have been on a stable dose and frequency for 7 days and show at least a 20% improvement in MFM 20 or 32 (depending on the age of patient) from Day 1 of Run-in.

Patients already receiving amifampridine phosphate treatment for CMS meeting the inclusion and exclusion criteria are eligible to participate in this study. They can be randomized into Period 1 if on stable dose and frequency for 1 week before being randomized to a Treatment Sequence. Improvement of at least 20% in MFM 20 or 32 is not a requirement for these participants.

Patients who are deemed eligible will be administered amifampridine phosphate for Day 0 at the study site, by the study personnel, and have the assessments/procedures listed below completed, in relation to the time of receiving study medication on Day 0, before randomization.

- Confirmation of Inclusion/Exclusion criteria;
- Assessment of AEs/SAEs;
- Abbreviated physical exam with weight;
- Vital signs (seated position), including SBP, DBP, heart rate, respiration, and body temperature;
- Clinical laboratory tests;
- Urine pregnancy test in females of childbearing potential only;
- Concomitant medications;
- IP accountability;
- Efficacy assessments, including:
 - MFM 20 or 32;
 - SGI (patient/parent/guardian/caregiver);
 - CGI-S;
 - CGI-I; and
 - Slurp test (optional).

Assessment	Start Time After Dose* (\pm 10 minutes unless otherwise specified)
SGI	40 minutes
MFM 20 or 32	after SGI
Slurp test, CGI-S and CGI-I	At end of assessments

*Administration of medication represents Time 0 (minutes)

The site pharmacy will dispense bottles containing blinded amifampridine phosphate or placebo tablets, depending on the patient's Treatment Sequence assignment, for daily outpatient administration for 7 days (Days 1-7). Administration of blinded study medication will begin with the next scheduled dose following the Day 0 baseline assessment on open-label medication. (see Section 13.3).

13.3 Period 1

Administration will be continued on an outpatient basis for a total of 7 days (Days 1-7).

On Day 8 (+1) patients will be given a dose of the same study medication as the previous 7 days by the study personnel, at the site, so that the assessments/procedures listed below will be completed in relation to the time of study medication dosing.

- Assessment of AEs/SAEs;
- Abbreviated physical exam with weight;
- Vital signs (seated position), including SBP, DBP, heart rate, respiration, and body temperature;
- Clinical laboratory tests;
- Concomitant medications;
- IP accountability;
- Efficacy assessments, including:
 - MFM 20 or 32;
 - SGI (patient/parent/guardian/caregiver);
 - Stimulated Single fiber EMG (optional);
 - CGI-S;
 - CGI-I; and

- Slurp test (optional).

Assessment	Start Time After Dose* (± 10 minutes unless otherwise specified)
SGI	40 minutes
MFM 20 or 32	after SGI
Stimulated Single fiber EMG	after MFM
Slurp test, CGI-S and CGI-I	At end of assessments

*Administration of medication represents Time 0 (minutes)

If the stimulated single fiber EMG (optional assessment) is not to be performed, then the slurp test (also optional), CGI-S and CGI-I assessments should be done following completion of the MFM.

Open-label amifampridine phosphate will be dispensed at the Day 8 visit for administration during the stabilization period, starting with the next scheduled dose after Day 8 assessments (see Section 13.4).

13.4 Re-stabilization Period

Patients will return to their prior open-label amifampridine phosphate dose established in the run-in phase for 2 weeks, Day 9 through Day 21.

Patients will report to the study site on Day 21 (+1 day) and have the assessments/procedures listed below completed.

- Assessment of AEs/SAEs;
- Abbreviated physical exam with weight;
- Vital signs (seated position), including SBP, DBP, heart rate, respiration, and body temperature;
- Urine pregnancy test in females of childbearing potential only;
- Concomitant medications;
- IP accountability;
- Efficacy assessments, including:
 - MFM 20 or 32;

- SGI (patient/parent/guardian/caregiver);
- CGI-S;
- CGI-I; and
- Slurp test (optional).

Assessment	Start Time After Dose* (\pm 10 minutes unless otherwise specified)
SGI	40 minutes
MFM 20 or 32	after SGI
Slurp test, CGI-S and CGI-I	At end of assessments

*Administration of medication represents Time 0 (minutes)

A The slurp test (optional), CGI-S and CGI-I assessments should be done following completion of the MFM.

The site will dispense bottles containing amifampridine phosphate or placebo tablets, depending on the patient's Treatment Sequence assignment, for Period 2 (Days 22-28). Administration of blinded study medication will begin with the next scheduled dose after Day 21 assessments are completed (see Section 13.5).

13.5 Period 2

Patients will the blinded study medication they did not receive in Period 1. Administration will be continued on an outpatient basis for a total of 7 days (Days 22-28).

Patients will report to the study site on Day 29 (+1 day) and receive a dose of the same study medication they received for the previous 7 days, under the supervision of the study personnel, in order to time the following assessments/procedures in relation to the medication dose.

- Assessment of AEs/SAEs;
- Complete physical exam with weight;
- Vital signs (seated position), including SBP, DBP, heart rate, respiration, and body temperature;
- Standard resting 12-lead ECG;
- Clinical laboratory tests;

- Urine pregnancy test in females of childbearing potential only;
- Concomitant medications;
- IP accountability;
- Efficacy assessments, including:
 - MFM 20 or 32;
 - SGI (patient/parent/guardian/caregiver);
 - Stimulated single fiber EMG (optional);
 - CGI-S;
 - CGI-I; and
 - Slurp test (optional).

Assessment	Start Time After Dose* (± 10 minutes unless otherwise specified)
SGI	40 minutes
MFM 20 or 32	after SGI
Stimulated Single fiber EMG	after MFM
Slurp test, CGI-S and CGI-I	At end of assessments

*Administration of medication represents Time 0 (minutes)

If the stimulated single fiber EMG (optional assessment) is not to be performed, then the slurp test (also optional), CGI-S and CGI-I assessments should be done following completion of the MFM.

After completion of the above procedures/assessments, patients will be eligible for an expanded access program.

13.6 Early Discontinuation Visit

Any patient that discontinues from the study, regardless of the reason, will be requested to complete all Early Discontinuation visit assessments/procedures as listed below after the last dose of IP. Every reasonable effort should be made to contact any patient who is lost to follow-up.

- Assessment of AEs/SAEs;
- Complete physical examination with weight;

 Catalyst <small>pharmaceuticals</small>	CMS-001 Version Amendment 5	Page 67
---	---------------------------------------	----------------

- Vital signs (seated position), including SBP, DBP, heart rate, respiration, and body temperature;
- Standard resting 12-lead ECG;
- Clinical laboratory tests;
- Urine pregnancy test in females of childbearing potential only;
- Concomitant medications;
- IP accountability; and
- Efficacy assessments, including:
 - MFM 20 or 32;
 - SGI (patient/parent/guardian/caregiver);
 - Stimulated Single fiber EMG (optional);
 - CGI-S;
 - CGI-I; and
 - Slurp test (optional).

The date of the last dose of study medication should be recorded in relation to Early Discontinuation assessments.

14 DATA QUALITY ASSURANCE

Catalyst personnel or designees will visit the study site before initiation of the study to review with the site personnel information about the IP, protocol and other regulatory document requirements, any applicable randomization procedures, source document requirements, CRFs, monitoring requirements, and procedures for reporting AEs, including SAEs.

At visits during and after the study, a CRA will monitor the site for compliance with regulatory documentation, with a focus on accurate and complete recording of data on CRFs from source documents, adherence to protocol, randomization (if applicable), SAE reporting and drug accountability records.

Data quality control and analysis will be performed by Catalyst or a designee, based on a predefined analysis plan.

 Catalyst <small>pharmaceuticals</small>	CMS-001 Version Amendment 5	Page 68
---	---------------------------------------	----------------

15 STATISTICAL METHODS AND DETERMINATION OF SAMPLE SIZE

15.1 Determination of Sample Size

Assuming a standardized between-treatment difference of 0.5, 23 patients per sequence will ensure power of 90% for the 2-sided test at the 0.05 level using the standard 2-by-2 crossover analysis.

15.2 Safety Analysis

Safety analyses will be conducted on the safety population (i.e. all patients who receive at least 1 dose of amifampridine phosphate or placebo). The safety analysis will be descriptive and will be presented on observed data only. All safety data, and corresponding Change From Baseline (CFB) if appropriate, will be listed.

15.3 Adverse Events

All treatment-emergent adverse events (TEAEs) will be summarized by the treatment at the time of onset. Counts and percentages will be presented by treatment for each observed system organ class (SOC) and preferred term (PT) as defined in MedDRA. Summaries by level of severity and relationship to treatment will be presented by treatment at the time of occurrence. Listings of all deaths, SAEs, and discontinuations due to AE will be provided.

15.4 Laboratory Tests

For each laboratory parameter, descriptive statistics will be presented for the observed value and CFB by treatment at the time of the assessment. The frequency and percentage of patients who experience abnormal (i.e. outside of reference ranges) laboratory values will be presented by treatment at the time of the assessment. Clinically significant abnormalities will be collected as AEs.

15.5 Other Safety Assessments

Summary statistics for vital signs, physical examinations, and ECG parameters will be presented by treatment at the time of the assessment.

15.6 Efficacy Analysis

The following provides a summary of the planned statistical analyses. Details will be provided in a separate Statistical Analysis Plan (SAP), which will be finalized prior to unblinding. Any inconsistency between the SAP and the protocol will be noted in the SAP.

Efficacy analyses will be performed for 2 datasets:

 Catalyst <small>pharmaceuticals</small>	CMS-001 Version Amendment 5	Page 69
---	--------------------------------	---------

Full Analysis Set (FAS): This population consists of all randomized patients who receive at least 1 dose of IP (amifampridine phosphate or placebo) and have at least one post-treatment efficacy assessment.

Per Protocol (PP): This population is a subset of the FAS population, excluding patients with major protocol deviations.

If the PP Population is the same as the FAS, then the results will be presented only for the FAS. Exclusion from the FAS and PP Population will be finalized prior to database lock and subsequent unblinding.

In addition to the following, summary statistics will be provided by treatment and period for CGI-I, CGI-S, Change From Baseline (CFB) for CGI-S, the optional Slurp Test, and variables associated with the optional SFEMG.

15.7 Primary Efficacy Analysis

The analysis of CFB for SGI is the primary efficacy analysis and will be performed using the standard analysis for a 2-by-2 crossover design. Summary statistics for SGI and CFB for SGI will be presented by treatment and period. P-values <0.05 will be considered statistically significant.

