15.8 Secondary Efficacy Analysis

The total score for MFM and the subtotal for each of the three dimensions (Standing and transfer, Axial and proximal motor function, and Distal motor function) will be standardized by the possible maximum for both MFM 20 and MFM 32. The CFB for these standardized scores will be analyzed using the standard analysis for a 2-by-2 crossover design for MFM 20 and MFM 32 separately and pooled, with the latter being the secondary and the separate analyses being supportive. The total scores, subtotals for each dimension, and the corresponding standardized scores will be summarized by treatment and period for MFM 20 and MFM 32 separately and standardized scores will be summarized by treatment and period for MFM 20 and MFM 32 pooled. P-values <0.05 will be considered statistically significant.

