1.3 Sample Size

The primary analysis variable is the SGI Change from Baseline (CFB). It will be analyzed using the standard analysis for a two-by-two crossover design. The sample size required to control the power depends on the ratio of the between-treatment difference and the standard deviation of the difference (that is, the effect size). Assuming an effect size of 0.5, 23 patients per sequence will ensure power of 90% for the 2-sided test at the 0.05 level.

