4.2 Analysis of Efficacy

4.2.1 Analysis of Primary Efficacy

Summary statistics for the SGI Day 0 assessment (baseline for period 1), SGI Day 8 assessment, and the corresponding change from baseline (CFB₁) will be presented by treatment and by treatment within mutation type (pre- vs. post-synaptic, see Table 2.2-1 above) as period 1. A Mann-Whitney-Wilcoxon test for equality of the CFB₁ in the two treatments in Period 1 will be presented. Summary statistics for the SGI Day 21 assessment (baseline for period 2), SGI Day 29 assessment, and the corresponding change from baseline (CFB₂) will also be presented by treatment and treatment within mutation type as period 2. Also, the change in CFB from Period 1 to Period 2 will be computed. This value estimates

$$\tau_1 - \tau_2$$

where τ_1 represents the treatment effect of the period 1 Investigational Product (IP) and τ_2 represents the treatment effect of period 2 IP. A Mann-Whitney-Wilcoxon test of the hypothesis that the above parameter is the same in both treatment sequences will be provided. Note that this is a nonparametric version of the treatment main effect in a linear model without carryover effects.

A mixed effects linear model will be fit to the data with SGI raw scores as the response. The model will include fixed effect terms for treatment, period, age group (2 to less than 6, 7 to less than 12, and 12 to less than 17 years of age, 17 years and over), mutation type and sequence*period, where sequence corresponds to the order in which the subject received treatments, and a random effect for subject. The LSMeans for the treatment groups will be calculated and provided, as will the estimated difference along with a 95% confidence interval for this difference and a formal hypothesis test that the difference in the means is 0.

Special care must be taken in crossover designs to ensure that there is not significant carryover effect; however, the pharmacological properties of amifampridine are such that

having a 12-day washout period should minimize any unequal carryover effects in the analysis.

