A mixed effects linear model will be fit to each of the MFM datasets described above with percent outcome or individual item scores (as appropriate for each dataset) as the response variable. The model will include fixed effect terms for treatment, period, age group (2 to less than 6 years, 7 to less than 12 years, 12 to less than 17 years of age, and 17 years of age and above), genetic mutation type (see Table 2.2-1), and sequence*period, where sequence corresponds to the order in which the subject received treatments, and a random effect for subject. No carryover term will be fit. In the case of the MFM percent outcome datasets for the adult only patients, the age group fixed effect term will not be included in the model. The LSMeans for the treatment groups will be calculated and provided, as will the estimated difference along with a 95% confidence interval for this difference and a formal hypothesis test that difference in the means is 0. Note that it is highly likely that some specific mutations will have insufficient subjects to fit the specified model. In that case a notation will be made in the relevant table(s) that there are not sufficient observations to fit the model.

Special care must be taken in crossover designs to ensure that there is no significant carryover effect; however, the pharmacological properties of amifampridine (an elimination half-life of 1.8-2.5 hours) are such that having a 12-day restabilization period will minimize any unequal carryover effects in the analysis.

Clinical Global Impression

CGI-S and CGI-I will be summarized by frequency tables and percentages for each sequence group and period. The values will be analyzed with a Wilcoxon rank-sum test as outlined in Putt and Chinchilli (2004). The treatment effects will be estimated using the Hodges-Lehmann estimator and a 90% asymptotic confidence interval.

Single Fiber Electromyogram

Summary statistics for mean jitter, median jitter, and percent block will be presented by treatment and visit. No formal inferential procedures will be performed for these data.

Slurp Test

Summary statistics for the time to slurp sound from the slurp test and its CFB (Day 0 for Period 1 and Day 21 for Period 2) will be presented. No formal inferential procedures will be performed for these data.

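### The SGI analyses either subtract the period baselines or ignore them; using them as a covariate would gain roughly 0 to 27 points of power at 23 patients, for one degree of freedom

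*Protocol*

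**What the plan says.** **Primary endpoint.** Protocol 15.7: "The analysis of CFB for SGI is the primary efficacy analysis and will be performed using the standard analysis for a 2-by-2 crossover design". SAP 1.3 also names SGI change from baseline (CFB) as the primary variable. SAP 4.2.1 takes Day 0 as baseline for Period 1 and Day 21 for Period 2, then adds: "Also, the change in CFB from Period 1 to Period 2 will be computed". That quantity is compared between sequences by a Mann-Whitney-Wilcoxon test. The same section also specifies a mixed model on raw SGI scores, with a confidence interval and a formal test. It does not say which of these decides.

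**Secondary endpoint.** Protocol 15.8 says of the MFM: "The CFB for these standardized scores will be analyzed using the standard analysis for a 2-by-2 crossover design". The SAP 4.2.2 mixed model instead uses the score itself, "with percent outcome or individual item scores (as appropriate for each dataset) as the response variable". The shells for Tables 15, 23 and 27 label the result as a mean change from baseline, while their footnotes say that the raw or percent score was modelled.

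**Sample size.** SAP 1.3: "Assuming an effect size of 0.5, 23 patients per sequence will ensure power of 90% for the 2-sided test at the 0.05 level". The effect size is "the ratio of the between-treatment difference and the standard deviation of the difference", given for the CFB variable. Planned enrolment is about 23 in total (Protocol Synopsis and 10.1; SAP 1.1).

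**Carryover.** SAP 4.2.1 relies on the statement that "having a 12-day washout period should minimize any unequal carryover effects in the analysis".

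**The concern.** In a two-period crossover each patient is already his or her own control, because the stable patient effect cancels in Day 8 minus Day 29. Day 0 and Day 21 are both scored on the same open-label dose, so their difference contains much within-patient noise. Subtracting it in full (slope 1) adds that noise to the contrast. Ignoring it (slope 0) discards whatever information it carries. A covariate lets the data choose the slope.

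What is at stake is precision from data already scheduled, in a rare-disease trial with no replacement of dropouts (Protocol 10.2.4) and complete-case analysis (SAP 2.3). A second issue is that Day 21 comes after randomisation. If patients given placebo first have not fully recovered by Day 21, that baseline differs by sequence, and each analysis handles the difference differently.

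**Working it through.** **Inputs.** From SAP 1.3: effect size 0.5 on the CFB contrast, two-sided 0.05, 23 per sequence. From Protocol and SAP: about 23 patients in total, allocated 1:1, so 11 + 12. Not in the documents, and therefore assumed over a range: r, the correlation between Day 0 minus Day 21 and Day 8 minus Day 29, and the ratio k of their variances.

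**1. Reproduce the stated power.** Compare within-patient period differences between sequences. The contrast is twice the treatment effect, so the noncentrality is 2 × 0.5 / √(1/n₁ + 1/n₂).
- 23 + 23: 1/√(2/23) = 3.39 with 44 df, power 91.2%. This matches the stated 90%.
- 11 + 12: 1/√(1/11 + 1/12) = 2.40 with 21 df, power 62.7%. This is the CFB figure at planned enrolment.

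**2. Variances.** Let V be the variance of Day 8 minus Day 29, and kV that of Day 0 minus Day 21.
- CFB (slope 1): V(1 + k − 2r√k)
- Unsubtracted (slope 0): V
- Covariate-adjusted: V(1 − r²)

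With k = 1 the ratio of CFB to adjusted variance is 2(1 − r)/(1 − r²) = 2/(1 + r).

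**3. Power at 11 + 12 with k = 1, holding the CFB effect size at 0.5** (CFB 62.7% throughout; adjusted analysis on 20 df):

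| r | Variance ratio 2/(1+r) | Adjusted power | Gain (points) |
|---|---|---|---|
| 0 | 2.00 | 89.6% | 27 |
| 0.3 | 1.54 | 80.7% | 18 |
| 0.5 | 1.33 | 74.9% | 12 |
| 0.7 | 1.18 | 69.6% | 7 |
| 0.9 | 1.05 | 64.8% | 2 |

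These figures charge one degree of freedom but not the sampling error of the fitted slope. Simulation including that error gives 88% at r = 0, 76% at r = 0.4 and 65% at r = 0.8, against 63% for CFB. With scores rounded to the 7-point scale with a ceiling, simulated power rises from 62% to 84% (r = 0), 59% to 73% (r = 0.3) and 56% to 66% (r = 0.5), with type I error 4.9%.

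**4. Unsubtracted contrast.** With k = 1 the ratio of CFB to unsubtracted variance is 2(1 − r). At r = 0 that gives 89.8% power, as good as adjustment. At r = 0.5 it equals CFB, and above 0.5 it is worse.

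**5. Baselines less variable than outcomes.** The only SGI SDs in the documents are from the LEMS study (Protocol 8.4.3): 1.2 at baseline and 2.3 for the change on placebo. They are between-patient figures from another disease, so illustrative only. Assuming zero covariance, the post-treatment variance is 2.3² − 1.2² = 5.29 − 1.44 = 3.85, and k = 1.44/3.85 = 0.374.
- r = 0: ratio 1.374, adjusted power 76%
- r = 0.3: (1.374 − 0.367)/0.91 = 1.107, 67%
- r = 0.5: (1.374 − 0.612)/0.75 = 1.017, 63%

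**6. Worst case for adjustment.** If r = √k, a slope of 1 is exactly right and the two variances are equal. The noncentral t gives 62.5% against 62.7%. With the cost of estimating the slope, the loss is about 2 points.

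**7. Incomplete recovery.** Suppose the placebo-first sequence is x points short at Day 21, and let b be the fitted slope.
- Recovered by Day 29: CFB shifts x/2 towards drug; the adjusted analysis shifts bx/2.
- Shortfall still present at Day 29: CFB cancels it; the adjusted analysis shifts (1 − b)x/2 against drug.

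**The case against.** A reader might infer that the primary analysis doubles the error variance and costs 27 points of power. The documents do not support that. Both figures need r = 0 and baseline differences as variable as outcome differences. Neither condition is documented, and the second is doubtful when both baselines are taken on stable drug while one outcome per patient follows withdrawal. Nor is anything lost against plan: SAP 1.3 defines the 0.5 on the CFB contrast, so its variance is already inside the effect size. The drop from 90% to 63% comes from 23 in total against 23 per sequence, which is a separate and larger problem.

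It can also be said that an unsubtracted SGI analysis is already listed under primary efficacy, and at r = 0 it loses essentially nothing. That stands, but the model is unranked and does worse than CFB once r exceeds 0.5 with equal variances. It moves the guess about r rather than removing it.

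Two further objections stand. A covariate cannot simply be added to a Mann-Whitney test, so the decisive test would have to change to a parametric model on a 7-point score. And a reader might infer that incomplete recovery always biases CFB towards drug by x/2. That holds only if recovery is complete by Day 29. Adjustment then reduces the bias (for b between 0 and 1) without removing it, and if the shortfall persists CFB is the less biased of the two.

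**Conclusion.** The point holds as an efficiency improvement of uncertain size. At 11 + 12 patients and a CFB effect size of 0.5, adjustment would raise power from 63% to between about 65% (r = 0.9) and 90% (r = 0) with equal variances, and to about 76% at r = 0 with the illustrative LEMS SDs. It would cost about 2 points if a slope of 1 is exactly right. The forgone gain is therefore roughly 0 to 27 points, a little less after the cost of estimating the slope. The small downside against a possibly large gain favours adjusting. The result rests on t-based power for a linear contrast and on an r that neither document gives.

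The plan also leaves open which SGI analysis decides, and the choice among slopes of 1, 0 or an estimated value should be made before unblinding. The carryover sentence gives no assurance as worded, because patients take open-label drug throughout the interval that it calls a washout.

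**What to change.** 1. In Protocol 15.7 and SAP 4.2.1, before unblinding, name one decisive SGI test: a linear model of Day 8 minus Day 29 on sequence (coded 0/1), with Day 0 minus Day 21 as covariate. The treatment effect is half the sequence coefficient, reported with its 95% CI. This replaces the Mann-Whitney test in that role. Keep the CFB, Mann-Whitney and raw-score analyses as supportive.
2. Specify the same model for pooled MFM percent scores in Protocol 15.8 and SAP 4.2.2, and make the labels and footnotes of Tables 15, 23 and 27 agree.
3. Report Day 21 minus Day 0 by sequence for SGI and MFM as a check on incomplete recovery. The Table 5 shell already gives the two SGI visits by sequence, but not their difference.
4. Reconcile the descriptions of the interval between periods: a 12-day washout (SAP 4.2.1), a 12-day restabilization (SAP 4.2.2), 14 days (SAP 1.2 and Protocol Synopsis), 2 weeks (Protocol 13.4), and Days 9–21, which count inclusively to 13. Say that patients are on open-label drug throughout.

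Cost: wording, one model statement, one residual degree of freedom, and reliance on a parametric model for a 7-point score. No new data are needed.
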